10 patients + 5 accompanying persons per clinic = 540 patients + 270 accompanying persons x 3 weeks = 2430:

Total = **2484**

Stage 2 Pilot: AGP Procedure Rooms

9 sessions

Up to 9 clinicians

10 patients per session per clinician = 90 patients

Total = **99**

Stage 2: AGP Procedure Rooms

27 clinicians x 2 hospitals = 54 clinicians

10 patients per session per clinician = 540 patients x 3 weeks = 1620

Total = **1674**

Stage 3 Pilot: Wards

3 days

Approximately 6 beds in 1 bay. As days may not be consecutive, aim for up to 18 patients

Day nurse & night nurse = 2 per day so **6** in 3 days

Day HCA and night HCA = 2 per day so **6** in 3 days

Up to 3 doctors per day = **9** in 3 days

Total = **18+6+6+9 = 39**

Stage 3: Wards

Each of the 2 hospitals has 6 bays, each bay containing 6 beds. This gives a total of 72 beds.

25% patient turnover rate (72×1.25) = approximately **90** patients in 3 days.

Day nurse & night nurse = 12 per 24 hour period, so **36** in 3 days

Day HCA and night HCA = 12 per 24 hour period, so **36** in 3 days

6 doctors per day = **18** in 3 days

Total = **90+36+36+18= 180**

For each stage, we will also speak to **up to 30** other staff members including estates, infection prevention and control, managers and other relevant staff groups in each hospital. We will conduct

	
ethnographic observations, and informal interviews with infection control leads, clinical and estates staff to consider use of ventilation devices, how they are deployed, how are they used, challenges and solutions to their use - and we will perform up to 15 semi-structured interviews with management leads, clinical and estates staff. With observations.
 
Total = 30 x 2 hospitals x 3 stages = 180
 
Overall total = 192+2484+99+1674+39+180+180= 4848 participants

Inclusion criteria:	
Clinicians working at relevant clinical testing environments (1st trial outpatient clinic room, 2nd trial AGP room, 3rd trial ward bay)
 
All patients (and accompanying persons) attending in those relevant clinical testing environments
 
The mixed method evaluation may include people working in estates teams, hospital managers and other healthcare staff.

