Air particle counters (APCs) will be installed next to participating clinicians and at up to 4 other fixed locations in the room or ward bay, to measure the average number of aerosol droplets per minute per clinical encounter. A clinical encounter is defined as *one* outpatient consultation, AGP procedure or ward session. A small aerosol-producing device(s) may also be installed within the room, if needed, as determined in the pilot phase.

To assess numbers of people in the rooms and amount of movement (each of which will impact airflows and infective respiratory particle numbers) an infrared camera will be used throughout to generate video heatmaps (figure 2). The camera will detect heat emanating from people in the room but will not be able to identify any individual person.

[figure not shown]

Figure 2. A heatmap of 2 people sitting on a park bench. Whilst it is possible to locate them precisely, it is not possible to identify them.

For the trial in the 3rd environment (in the ward bays with approximately 6 beds), the trial will be run on 3 consecutive days. As with the other 2 stages, the configurations will be different on each day, to allow direct comparisons. The AISaT will be turned on and air quality safety measures will be implemented, turned off completely with no extra air quality safety measures or air quality safety devices (such as filters, fans and screens etc.) given to the senior nurse on the ward to use and place as they see fit. The daily order of these 3 different configurations will be randomised.

This trial will be conducted across 12 ward bays (6 in each hospital). APCs will be installed next to each bed in the ward.

Running alongside the trial will be mixed methods implementation studies. These will include exploratory research interviews and usability testing in the pilot phase and process evaluation during the main RCT stages.

STOP-GO Criteria

Each trial is due to complete within 6 months, with a 3-month buffer to deal with unforeseen problems.

STOP CRITERIA:

1. The pilot phase for the first trial in consulting rooms will recruit 20% of the patients in 5 weeks.

The trial will STOP if we don't recruit 60% of expected number (i.e. 12% of the total recruitment).

a. Management:

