For trial stage 3 and its pilot, a total of 12 patient bays is required, 6 at each hospital and each will participate for 3 days. There is no formal sample size calculation for stage 3, as it requires inputs that we do not possess at the moment, including the correlation between the measurements within a bay, as well as the correlation over time. The design is a cluster randomised cross-over control trial. Given that there are 6 possible sequences of the 3 configurations, we chose 12 bays so that there are 2 bays per sequence.

Decisions about wards will be driven by senior clinical management. In wards, if patients accept the study, they will be in the bay until they are discharged, so no drop out is expected. Recruitment of other hospital staff to join the implementation science elements of the study is expected to be around 8-10 per month across the two sites for the duration of the study.

Loss to follow up is not considered to be relevant as participation is only for a very short period of time.

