10.5 Randomisation methods

In study stages 1 and 2, clinicians will be randomised using simple randomisation to the order of the three different interventions. In study stage 3, ward bays will be randomised using simple randomisation. Each clinician or ward bay acts as its own control. Randomisation will be implemented using random permuted blocks. [name], Head of Statistics at the Comprehensive Clinical Trials Unit at UCL, will be in charge of randomisation using standard CCTU approaches.

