10.10 Sensitivity and other planned analyses

At the end of the clinic, a member of the research staff will ensure that there was compliance to the randomised setting and a log will be kept in order to track this data. The measurements will be reviewed for reliability.

At the end of each pilot phase, an interim statistical analysis will be performed to assess whether the main study is likely to meet the study goals.

Data analysis will be linear mixed modelling of the data controlling for confounding factors. Sensitivity analyses will remove measurements that are considered potentially, or definitely, unreliable. These analyses will be compared to the analyses that keep all collected data points. Interpretation of the main findings

Full data analysis will be undertaken by our co-I at CCTU and his team at the end of each stage of the clinical trials and will again perform data analysis using linear mixed modelling of the data (3 conditions for each clinician) controlling for confounding factors.

Decision criteria used to judge the interim results as part of a guideline for early stopping

Each trial is due to complete within 6 months, with a 3 month buffer to deal with unforeseen problems. The pilot phase for the first trial in consulting rooms will recruit 20% of the patients in 5 weeks. The trial will STOP if we don't recruit 60% of expected number (i.e. 12% of the total recruitment).

The AlSaT tool may not be able to compute a solution to reduce aerosol transmission in the rooms we wish to use for trial. If this occurs, the TMG will allow an extra 3 months to find rooms that the tool can be used in. If we cannot find suitable clinic rooms, TMG will stop the trial.

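### Stage 3 randomises ward bays, but the only stated primary model, repeated for the end of every stage, pairs the three conditions by clinician

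*Protocol*

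**What the plan says.** **Design and randomisation.** Protocol 10.4 says of Stage 3: "The design is a cluster randomised cross-over control trial". It gives no formal sample size for that stage because the correlations within a bay and over time are not yet known. The number of bays follows from the six possible sequences: "we chose 12 bays so that there are 2 bays per sequence". Section 10.5 adds "In study stage 3, ward bays will be randomised using simple randomisation" and "Each clinician or ward bay acts as its own control".

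**Analysis.** Section 10.8 gives one primary model for the whole programme, a linear mixed model of paired data in which the pairing is three conditions per clinician. The section is meant to cover Stage 3, because it sets a minimum of 6 hours of data per ward day and a day/night subgroup analysis for that stage. It does not change the pairing unit. Section 10.10 states that full analysis takes place "at the end of each stage of the clinical trials", and that the team "will again perform data analysis using linear mixed modelling of the data (3 conditions for each clinician".

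**Other places.** Section 4 states that randomisation is by clinician, with no exception for wards. The ward schedule in Appendix 2 has a row for clinician randomisation. By contrast, the missing-data text in 10.10 names clinicians or ward bays as the units for the complete-case analysis.

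**Ward staff and counters.** The Study Summary's Stage 3 headcount includes "Day nurse & night nurse = 12 per 24 hour period", multiplied to 36 over three days. Section 4 says of the ward stage "APCs will be installed next to each bed in the ward".

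**The concern.** In Stages 1 and 2 the clinician is the randomised unit, the repeated unit and the pairing unit, so the model wording fits. In Stage 3 the bay takes all three roles, but the wording of the model does not change with it.

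A crossover gains its precision by comparing configurations within the unit that received all of them. If the grouping effect is the clinician and a bay has several staff across shifts, the groups in the model are not the randomised units. If a clinician is present for only one of the three days, that group holds a single configuration and contributes no within-unit comparison. The analysis then rests on differences between groups, and bay-to-bay variation, which the design was meant to remove, stays in the error.

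The stakes are higher in Stage 3 than elsewhere. It has 12 units and no sample size calculation, so the within-bay comparison is its main source of precision. An analysis plan that followed 10.8 and 10.10 literally would not analyse by the randomised unit. One that corrected them would depart from the protocol.

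**Working it through.** **1. The units, side by side**

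| Item | Stages 1–2 | Stage 3 | Protocol section |
|---|---|---|---|
| Randomised unit | clinician | ward bay | 10.5 |
| Own control | clinician | ward bay | 10.5 |
| Complete-case unit | clinician | ward bay | 10.10 |
| Pairing unit in the stated model | clinician | clinician (unchanged) | 10.8, 10.10 |

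Only the last row is out of line, and only for Stage 3.

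**2. Can a ward clinician stand in for the bay?** For the single bay of the Stage 3 pilot, the Study Summary lists a day nurse and a night nurse, a day and a night healthcare assistant, and up to three doctors per day. That is up to 2 + 2 + 3 = 7 staff per bay-day. For the main stage it counts nurses, healthcare assistants and doctors per day and multiplies each by three (12 to 36, 12 to 36, 6 to 18). Under configuration 3 the senior nurse for the ward decides on placement, and the protocol does not tie that nurse to one bay. No clinician is shown to correspond one-to-one with a bay.

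**3. Reproducing the plan's own figure.** Inputs from 10.3: means 0, 0.25, 0.5; SD 1; correlation ρ = 0.5 with compound symmetry; α = 0.05; 90% power.

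- Sum of squared deviations of the means from 0.25: 0.0625 + 0 + 0.0625 = 0.125.
- Noncentrality: λ = n × 0.125 / (1 − ρ) = 0.25n at ρ = 0.5, with 2 and 2(n − 1) degrees of freedom.
- n = 52 gives power 0.899; n = 53 gives 0.905; n = 54 gives 0.911.

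The stated 53, raised to 54, reproduces. That calculation has the clinician as repeated unit, so it applies to Stages 1 and 2 only.

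**4. Illustration for Stage 3.** The protocol gives no Stage 3 inputs. Assumptions: the same means and SD, n = 12 bays, one value per bay-day, within-bay correlation 0.3 to 0.7.

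*Paired by bay:* λ = 12 × 0.125 / (1 − ρ) = 1.5 / (1 − ρ), with 2 and 22 degrees of freedom.

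*No bay term:* a one-way F-test with 2 and 33 degrees of freedom on the same correlated data, by simulation. Under the null its numerator has expectation 1 − ρ while its denominator has expectation 1, so the test is conservative. It uses a contrast variance too large by the factor 1 / (1 − ρ).

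| ρ (assumed) | λ, paired | Power, paired by bay | Power, no bay term | Type I error, no bay term | 1 / (1 − ρ) |
|---|---|---|---|---|---|
| 0.3 | 2.14 | 21% | 11% | 1.7% | 1.43 |
| 0.5 | 3.00 | 28% | 7% | 0.5% | 2.00 |
| 0.7 | 5.00 | 45% | 4% | 0.1% | 3.33 |

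Even correctly paired, power is modest under these borrowed inputs. That part comes from having 12 bays, not from the model wording.

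**The case against.** The strongest reply is that the protocol already fixes the bay as the Stage 3 unit. Section 10.4 calls the design cluster randomised, 10.5 names the bay as its own control, and 10.10 lists ward bays among the complete-case units. The clinician wording then looks like Stage 1 and 2 text carried forward, and a statistician reading the whole document would pair by bay. This stands as an account of intent, and it limits the likely harm. It does not make 10.8 and 10.10 correct, since the model they state names a unit and for Stage 3 it is the wrong one.

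The size is also fairly challenged. A model with no bay term is not a mixed model of paired data, the planned adjustment for ventilation, room size and room shape could absorb part of the between-bay variance, and the correlations are assumed. All of that stands, so the figures show a worst case.

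A reader might infer two stronger things that the documents do not support.

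- *That the plan has different nurses each day.* The 36 is a recruitment headcount obtained as 12 × 3. The Study Summary and section 4 give ward clinicians' participation as 3 days. Daily turnover is neither stated nor needed: several staff on separate shifts are enough to make the clinician wording fail to identify the bay.
- *That the bed counters are analysed as independent observations, inflating false positives.* The protocol does not say this. Its outcome (3.3, 10.1) is an average per clinical encounter, and a ward session is one encounter, which is compatible with a single summary per session.

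Degrees-of-freedom corrections and the detailed random-effects structure can be left to the statistical analysis plan.

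**Conclusion.** The point holds as a contradiction within the protocol. Stage 3 is randomised and controlled by bay, while the only stated primary model, repeated for the end of every stage, pairs by clinician. Followed literally, the model would not analyse by the randomised unit or use the within-bay comparison.

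The cost cannot be computed from the documents, because the Stage 3 correlations are unknown. On the illustrative inputs, dropping the bay term altogether reduces power from 21%–45% to 11%–4% and takes the type I error from 5% down to about 2%–0.1%. The direction is therefore lost sensitivity, not excess false positives. If the same staff were present on all three days, grouping by clinician could retain some of the pairing and the loss would be smaller.

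This is a correction worth making before Stage 3 is analysed. It is not a flaw in the Stage 3 design.

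**What to change.** - In 10.8 and 10.10, state the pairing as three conditions for each clinician (Stages 1–2) or for each ward bay (Stage 3), with bay as the grouping effect in Stage 3.
- State that the Stage 3 outcome is summarised once per bay-day, or that the counters of one bay-day are otherwise kept together in the model.
- In section 4, extend the sentence on randomisation by clinician to say that ward bays are randomised in Stage 3.
- In Appendix 2, replace the clinician randomisation row with bay randomisation.

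The cost is a wording amendment. No new data, extra bays or change in conduct is needed, and Stage 1 and 2 analyses are unaffected.

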10.3 Sample size calculation

Participants: 3 consulting rooms or 3 AGP rooms in each hub hospital. 54 clinicians who regularly use these rooms (27 per hospital approximately) will be invited to take part, each for 3 consecutive weeks.

A 3-period, 3-treatment cross-over design will be used to test whether there is a difference in the 3 means. The comparison will be made using a Geisser-Greenhouse corrected F-test with a Type I error rate (α) of 0.05. The group means under the null hypothesis are assumed to be equal. The standard deviation across subjects at the same period is assumed to be 1 (and the means are expressed, see below, as a fraction of the standard deviation, which allows us to calculate a sample size using the Cohen's D approach). The assumed pattern of the covariance matrix is 'all correlations equal' (compound symmetry) with a correlation of 0.5 between adjacent time point measurements. To detect group means of '0 0.25 0.5' with 90% power, the needed number of clinicians is 53 (each measured 3 times). Given that there are six possible sequence combinations of the 3 treatments, the sample size is increased to the closest multiplicator of 6, which is 54. The sample size was computed using PASS 2024, version 24.0.2.

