10.8 Primary outcome analysis

Data analysis will be linear mixed modelling of the paired data (3 conditions for each clinician) controlling for confounding factors which may include: number of people in the room, baseline ventilation, room size, room shape, temperature, humidity and various other factors (see full list of suggested confounding factors in study design section). The power of the trial based on the UK sites alone is 90%.

Data analysis relies on properly functioning aerosol generators and particle counters. In stages 1 and 2, we will check each piece of machinery is working properly before the beginning of the clinical session. Where we do not manage to collect data for at least 2 hours in a clinical session, that session will be withdrawn from the study and repeated in its entirety. We expect this to happen in less than 5% of clinic sessions. For stage 3, a minimum of 6 hours data per day is required otherwise that day's randomisation will need to be rerun.

There are no plans for predefined subgroup analyses in stages 1 and 2. For stage 3, subgroup analyses will include daytime (8 am to 8pm) versus nighttime (8 pm to 8 am).

We will employ the intention-to-treat (ITT) analysis method to ensure the integrity and validity of our RCTs.

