The strategies to maximise follow-up and prevent missing data

No follow-up is required. We will collect only essential information to reduce participant burden. Strategies to minimise the risk of missing data include ensuring that CRFs are user-friendly, and electronic CRFs will have mandatory data fields and data validation checks. We will also provide

thorough training to the clinical trials staff to ensure that they check CRF data at the time they are completed. The pilot study phases will also identify potential issues before the main studies begin.

How recording of reasons for missing data will be undertaken

Recording reasons for missing data will be undertaken using standardised forms to capture these reasons. The forms will be developed and iterated throughout the pilot phases and as the trials progress. Study personnel will also be trained regularly and encouraged throughout the trials to document reasons for missing data in a detailed way. This includes noting the specific circumstances and any relevant participant feedback when data is missed.

Where participant interviews are undertaken, follow-up interviews will be offered to those who miss appointments or data collection points. This will help the study team gather insights into the reasons for missing data and address any issues that may prevent future participation.

Finally, regular monitoring and audits will be undertaken to review the completeness and accuracy of the recorded reasons for missing data.

How missing data will be handled in the analysis and whether there are any planned methods to impute missing outcome data, including which variables will be used in the imputation process

Initially, we will perform a complete-case analysis, where only participants (clinicians or ward bays) with complete data from all entire study periods are included. This approach helps to understand the extent and pattern of missing data. We will then conduct sensitivity analyses to assess the impact of missing data on our results. This includes comparing the results of complete-case analysis with those obtained using imputation methods.

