We will use multiple imputation (MI) to handle missing data. MI involves creating multiple datasets by imputing missing values based on observed data, analysing each dataset separately, and then combining the results to produce final estimate. Full information maximum likelihood (FIML) will be used as an alternative method, which estimates model parameters directly using all available data without imputing missing values.

The imputation process will include the following variables to ensure accurate and unbiased estimates: **Baseline Characteristics:** Age range, sex, body size, **Outcome Measures:** Primary outcome measure of respiratory particle counts. **Auxiliary Variables:** Additional variables that are correlated with the missing data and the outcomes, such as environmental factors and room conditions will be analysed.

The procedure for reporting any deviation(s) from the original statistical plan

We will document deviations, including details of the nature, reason and potential impact of the deviation on the study outcomes.

Significant deviations that may affect the study validity, reliability, or participant safety will be reported immediately to the TMG and the study sponsor and will also be reported to the TSC. The PI and local study team will conduct an assessment and root cause analysis of the deviation. This involves identifying who deviated from the protocol, what the deviation was, when and how it occurred, and its impact on the study. Based on the assessment, an action plan will be developed to address the deviation. This plan will include steps to mitigate any negative impact and prevent similar deviations in the future.

Minor deviations (which are not considered to be adverse events for participants) will be documented and reported to the TMG during regular progress reports. All deviations and the corresponding action plans will be transparently reported in the final study report and any publications resulting from the study to make the scientific community aware of changes to the original statistical plan.

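### Section 10.10 leaves it unclear which missing-data analysis has precedence, starts by dropping incomplete clinicians despite the ITT promise, and does not name the randomised configuration in its imputation list

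*Protocol*

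**What the plan says.** Section 10.8 gives the primary analysis as a linear mixed model of the three conditions for each clinician, and adds: "We will employ the intention-to-treat (ITT) analysis method to ensure the integrity and validity of our RCTs". It also sets a repeat rule. A Stage 1 or 2 session with less than two hours of data is withdrawn and repeated, which is expected for fewer than 5% of sessions. A Stage 3 day with less than six hours of data is rerun.

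Section 10.10, under how missing data will be handled, begins: "Initially, we will perform a complete-case analysis, where only participants (clinicians or ward bays) with complete data from all entire study periods are included". The reason given is that this shows how much is missing and in what pattern. Sensitivity analyses then compare the complete-case result with imputed results. The next paragraph says MI will be used for missing data, with the pooled results giving the final estimate, and that FIML on all available data will be an alternative.

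Of the imputation model, section 10.10 says: "The imputation process will include the following variables to ensure accurate and unbiased estimates". The variables named are age range, sex, body size, the particle count, and auxiliary variables, with environmental factors and room conditions as examples. Configuration, period and clinician or bay are not named.

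**The concern.** There are two problems.

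**Precedence.** Three analyses are described: complete-case, MI and FIML. Complete-case comes first and is the reference for the sensitivity analyses, MI is said to give the final estimate, and FIML is an alternative. A reader cannot tell which is the trial's result. The one that comes first is also the one that departs from the ITT promise. It removes a randomised clinician or bay with two valid periods, although the mixed model in section 10.8 can use those two periods directly. An unsettled choice among three analyses could be made after the results are seen.

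**The imputation list.** The quantity to be imputed is a session's or day's particle count, and its main designed source of variation is the configuration. If configuration is not in the imputation model, imputed values carry no configuration effect and pull the contrast towards zero. The list is said to secure unbiased estimates, and read literally it does not.

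**Working it through.** **1. Reproduce the planned sample size.** Inputs are from section 10.3: "with a Type I error rate (α) of 0.05", "To detect group means of '0 0.25 0.5' with 90% power", "The standard deviation across subjects at the same period is assumed to be 1", and compound symmetry "with a correlation of 0.5 between adjacent time point measurements".

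- Mean of 0, 0.25 and 0.5 is 0.25; sum of squared deviations = 0.0625 + 0 + 0.0625 = 0.125.
- Noncentrality λ = n × 0.125 / (1 × (1 − 0.5)) = 0.25n, with 2 and 2(n − 1) degrees of freedom (no sphericity correction is needed under compound symmetry).
- Power is 89.9% at n = 52, 90.5% at n = 53 and 91.1% at n = 54.

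The stated 53, rounded up to 54, reproduces.

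**2. Complete-case against all available periods.** Assume a fraction m of sessions is missing independently and completely at random, and is not recovered by repeats. The protocol gives no such rate; m = 5% is used because section 10.8 expects fewer than 5% of sessions to fail.

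- Complete clinicians: 54 × 0.95³ = 54 × 0.857 = 46.3.
- Complete-case: λ = 0.25 × 46.3 = 11.57, power about 86% (85.7% at n = 46).
- All available periods: with correlation 0.5, a clinician contributes information on the configuration contrasts of 2 with three periods, 10/9 on average with two, and 1/3 with one. The expected shares are 0.95³ = 0.8574, 3 × 0.05 × 0.95² = 0.1354 and 3 × 0.05² × 0.95 = 0.0071.
- λ = 54 × 0.125 × (2 × 0.8574 + 10/9 × 0.1354 + 1/3 × 0.0071) = 6.75 × 1.8675 = 12.61.
- Denominator degrees of freedom are about 162 × 0.95 − 54 − 2 = 98. Power is about 89%.

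The avoidable loss is about 3 percentage points. In Stage 3, one dropped bay is 1/12 = 8.3% of the sample.

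**3. Imputation without configuration.** Suppose each session is one row and missing values are drawn from a model without configuration. Imputed sessions then have the same expected value in every configuration. With a fraction m imputed, the expected contrast is (1 − m) × 0.50 SD: 0.475 at 5%, 0.45 at 10% and 0.40 at 20%.

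A simulation agrees (54 clinicians, correlation 0.5, missing completely at random, 10 imputations, 1,500 replicates, Monte Carlo standard error about 0.004):

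| Sessions missing | MI without configuration | MI with configuration | Complete-case |
|---|---|---|---|
| 5% | 0.479 | 0.504 | 0.504 |
| 10% | 0.450 | 0.499 | 0.499 |
| 20% | 0.401 | 0.501 | 0.500 |

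Adding configuration alone removes the attenuation. The complete-case estimate is unbiased here, so its cost is precision.

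**The case against.** The strongest reply is that the protocol already contains the right tools. FIML uses all available data and has no imputation model to mis-specify, and section 10.8 already plans a mixed model. Complete-case is given a descriptive purpose and is nowhere called primary; the text gives an order, and MI and FIML both keep incomplete clinicians. The auxiliary category is open-ended. Imputing in wide format, with one outcome column per configuration, would carry configuration and clinician implicitly. A full imputation model commonly sits in a statistical analysis plan, which is not at hand. Finally, the repeat rule limits how much will be missing.

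Most of this stands, and it limits the size of the point. It does not settle precedence: the protocol itself fixes an order, a reference analysis and a variable list, and these do not agree with each other or with section 10.8.

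A reader might infer more than the documents support:

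- **That the imputed contrast will be biased.** It will be only if the list is followed as written and imputation is by session.
- **That omitting clinician and period also drives the contrast to zero.** Omitting clinician mainly costs precision, and period matters little if sequences are balanced.
- **That attenuation could reach 14%.** That figure, 1 − 0.95³, is the share of clinicians with any missing session; the share of sessions imputed is still 5%.
- **That the 5% clinician dropout in section 10.4 is a cost of complete-case.** It leaves 54 × 0.95 = 51.3 clinicians (89.3% power at n = 51), but a clinician with no data contributes nothing under any analysis.
- **That complete-case selects on how disruptive a configuration was.** This is possible but not shown. Section 10.4 relates dropout to cancelled clinics, and section 10.8 discusses lost data in terms of working equipment.

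**Conclusion.** The point holds as a minor one. Section 10.10 is contradictory on which analysis has precedence, and the analysis it puts first does not fit the ITT mixed model of section 10.8. The imputation list does not name the factor whose effect is being estimated.

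If 5% of sessions were lost and not recovered, complete-case would cost about 3 points of power, and session-level imputation from the literal list would cost about 5% of the effect, or 0.02 to 0.03 SD. Both rest on missingness completely at random and on the assumed rate. The power comparison also rests on the section 10.3 variance and correlation. If repeats recover most failed sessions, both effects are smaller. Even the all-available-data model falls slightly below 90% at 5% missing, so the fix recovers most of the loss but not all of it.

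The precedence question matters more in Stage 3, where there are 12 bays and section 10.4 gives no formal sample size.

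**What to change.** In sections 10.8 and 10.10, state that the primary analysis is the linear mixed model fitted by ML or REML to all available periods of every randomised clinician or bay, analysed as randomised, with configuration and period as fixed effects and clinician or bay as random. This is the likelihood approach section 10.10 already names as FIML. It is valid when data are missing at random given what the model contains.

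Make complete-case a sensitivity analysis. If MI is kept, label it a sensitivity analysis too, and include configuration, period and clinician or bay in the imputation model.

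The change is to wording only, in the protocol and in the statistical analysis plan if there is one. It needs no further data, participants or time.
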